6.3.3 Early Termination Visit

The following activities may be performed at the early termination visit for subjects who withdraw, or are withdrawn or terminated from this study:

- Obtain vital signs (BP, HR, and oral temperature) (if needed)
- Perform symptom-directed PE (if needed)
- Evaluate vaccination site if within Day 15 after each vaccination
- Review Unsolicited AEs if within Day 29 after each vaccination
- Review of SAEs.
- If occurring through Day 8 after any vaccine dose, interview the subject and review the e-Memory aid data. Address any incomplete, missing, or inconsistent data. If visit occurs between Day 8 and Day 29, if needed the subject will be interviewed and ongoing solicited AEs will be reviewed.
- If symptoms persist post Day 8, clinic staff will attempt to follow up with the subject daily until the symptoms resolve. Maximum severity post Day 8 and stop date of the symptoms will be recorded by clinic staff on the Solicited Events eCRF.
- Review concomitant medications.
- Obtain blood for safety laboratories (if needed)
- Obtain serum for immunogenicity assays (if needed)

```
DMID/NIAID/NIH
```

- Collect PBMCs and plasma for future assays (if needed).
- Review of birth control history with female subjects.
- Counsel subjects to use adequate birth control methods to avoid pregnancy if before 3 months after the last study vaccination
- A urine pregnancy test for women of childbearing potential may be performed.

6.4 Unscheduled Study Visits

Unscheduled visits may occur at any time during this study. Any of the following activities may be performed:

- Obtain vital signs (BP, HR, and oral temperature) (if needed)
- Perform symptom-directed PE (if needed)
- Evaluate vaccination site if within Day 15 after each vaccination
- Review Unsolicited AEs if within Day 29 after each vaccination
- Review of SAEs.
- If occurring through Day 8 after any vaccine dose, interview the subject and review the e-Memory aid data. Address any incomplete, missing, or inconsistent data. If visit occurs between Day 8 and Day 29, if needed the subject will be interviewed and ongoing solicited AEs will be reviewed.
- If symptoms persist post Day 8, clinic staff will attempt to follow up with the subject daily until the symptoms resolve. Maximum severity post Day 8 and stop date of the symptoms will be recorded by clinic staff on the Solicited Events eCRF.
- Review concomitant medications.
- Obtain blood for safety laboratories (if needed)
- Obtain serum for immunogenicity assays (if needed)
- Collect PBMCs and plasma for future assays (if needed).
- Review of birth control history with female subjects (if needed).
- Counsel subjects to use adequate birth control methods to avoid pregnancy if before 3 months after the last study vaccination.
- A urine pregnancy test for women of childbearing potential may be performed.

DMID/NIAID/NIH

Phase I Study of HEV-239

6.5 **Protocol Deviations**

A protocol deviation is any noncompliance with the clinical trial protocol, GCP, or protocolspecific MOP requirements. The noncompliance may be either on the part of the subject, the site principal investigator, or the site personnel. As a result of deviations, corrective actions are to be developed by the site and implemented promptly.

These practices are consistent with ICH E6:

- 4.5 Compliance with Protocol, Sections 4.5.1, 4.5.2, and 4.5.3
- 5.1 Quality Assurance and Quality Control, Section 5.1.1
- 5.20 Noncompliance, Sections 5.20.1, and 5.20.2.

It is the responsibility of the site principal investigator and personnel to use continuous vigilance to identify and report deviations within five working days of identification of the protocol deviation, or within five working days of the scheduled protocol-required activity. All deviations must be promptly reported to DMID per the DCC protocol deviation reporting procedures.

All protocol deviations, as defined above, must be addressed in study subject data collection forms. A completed copy of the DMID Protocol Deviation Form must be maintained in the Regulatory File, as well as in the subject's chart. Protocol deviations must be sent to the local IRB/IEC per their guidelines. The site principal investigator and personnel are responsible for knowing and adhering to their IRB requirements.

DMID/NIAID/NIH

7 DESCRIPTION OF CLINICAL AND LABORATORY EVALUATIONS

7.1 Clinical Evaluations

7.1.1 Research Procedures: Medical History

Complete medical history will be obtained by interview of the subjects at the Screening Visit. Subjects will be queried regarding a history of significant medical disorders of the head, eyes, ears, nose, throat, mouth, cardiovascular system, lungs, gastrointestinal tract, liver, pancreas, kidney, urologic system, nervous system, blood, lymph nodes, endocrine system, musculoskeletal system, skin, and genital/reproductive tract. A focused vaccination history will be obtained. A history of any allergies, cancer, immunodeficiency, psychiatric illness, substance abuse, and autoimmune disease will be solicited. History of receipt of medications which modify the host immune response (e.g., cancer chemotherapeutic agents, parenteral corticosteroids), any experimental therapeutic agent, and blood product or immunoglobulin receipt will be solicited. A history of use of contraception will be solicited. Interview of subjects is sufficient for obtaining medical history. Solicitation of medical records from the subject's primary care provider is not required. Pre-vaccination reactogenicity symptoms will be solicited and recorded.

7.1.2 Research Procedures: Physical Examination

At the screening visit, an abbreviated physical examination will be performed by a study clinician licensed to make medical diagnoses and listed on the Form FDA 1572 as the site PI or sub-investigator. An abbreviated PE is distinguished from a complete PE as all assessments are not required (e.g., pelvic, rectal). The abbreviated PE will include assessments of the following organs and organ systems: skin, HEENT, neck, lungs, heart, liver, spleen, abdomen, extremities, lymph nodes (axillary and cervical), and nervous system. On Day 1 and at follow-up visits after the first study vaccination a symptom-directed PE may be performed by a study clinician licensed to make medical diagnoses and listed on the Form FDA 1572 as the site PI or sub-investigator, if indicated based on subject's interim medical history. This symptom-directed PE will be performed as indicated by the investigator based on any clinically relevant issues, clinically relevant symptoms and medical history. The symptom-directed PE may be repeated if deemed necessary by the investigator. Any abnormal finding that represents an increase in toxicity grade post study vaccination must be recorded on the AE page of the eCRF. All events should be followed to resolution, or until reaching a clinically stable endpoint.

DMID/NIAID/NIH

7.1.3 Research Procedures: Vital Signs

Vital signs (oral temperature, pulse, and BP) will be collected at the Screening Visit, and prior to and at a minimum of 30 minutes after each study vaccination (Day 1, Day 29, and Day 180). Vital signs assessed on Day 1 prior to the first study vaccination will be considered as baseline. Vital signs will also be assessed at Days 8, 15, 36, 43, 187, and 194 in all subjects. Blood pressure and heart rate measurements should be preceded by at least 5 minutes of rest in a quiet setting without distractions (e.g., television, cell phones). Confirmatory vital sign measurements can be repeated once. Subjects must not eat or drink anything hot or cold, or smoke within 10 minutes prior to taking oral temperature. The repeated measurement may be used to determine eligibility per the judgment of the investigator. Height and weight will be collected at the Screening Visit for the calculation of BMI. See the protocol specific MOP for additional details.

7.1.4 Research Procedures: Post Vaccination

Subjects will be observed in the clinic for at least 30 minutes after each study vaccination (Days 1, 29, and 180). Vital signs will be obtained at a minimum of 30 minutes after each study vaccination. The study vaccination site will be examined, post-reactogenicity symptoms will be recorded, and any AE/SAEs will be assessed and recorded on the appropriate eCRF prior to discharge from the clinic. The study vaccination site will also be examined at follow-up visit Day 8 after each study vaccination. The study vaccination site will be examined at follow-up visit Day 15 after each study vaccination as well, if needed.

All subjects will enter reactogenicity symptoms via an e-Memory aid to the SDCC beginning on the evening of the day of vaccination (Day 1, Day 29, and Day 180) through Day 8 after each study vaccination. Subject e-Memory aids will be reviewed with the subject for AEs on Days 4 (by telephone), Day 8, and if needed on Day 15 after each study vaccination. Reactogenicity assessments will include an assessment of solicited AEs including an assessment of injection site reactions of pruritus (itching), ecchymosis (bruising), erythema (redness), induration (hardness)/swelling, pain, and tenderness as well as systemic reactions including fever, feverishness (chills/ shivering/ sweating), fatigue (tiredness), malaise (general unwell feeling), myalgia (body aches/muscular pain exclusive of the injection site), arthralgia (joint pain exclusive of the injection site), headache, nausea, and vomiting.

DMID/NIAID/NIH

CONFIDENTIAL

7.1.5 Assessment of Concomitant Medications/Treatments other than Study Product

Medications history (concomitant medications) will include a review of all current medications and medications taken within 30 days prior to signing the informed consent form through Day 57, or Day 29 for those who only receive one dose of study vaccine, or early termination (if prior to Day 29 after any study vaccine dose), whichever occurs first. Concomitant medications will also include all current medications and medications taken within 30 days prior to Vaccine Dose 3 (Day 180) through Day 208. Concomitant therapies outside these times should only be recorded if administered in conjunction with SAEs. Prescription and over-the-counter drugs and vaccines will be included as well as vitamins, herbals, and supplements. Assessment of eligibility will also include a review of all permitted and prohibited medications per the Subject Inclusion and Exclusion Criteria (see Section 5.1.1 and 5.1.2).

Medications that might interfere with the evaluation of the investigational product should not be used unless necessary. Medications in this category include, but are not limited to, glucocorticoids (i.e., oral, parenteral and high-dose inhaled steroids), and immunosuppressive or cytotoxic drugs. Analgesics and antipyretics should be avoided for the 24 hours following study injection, unless necessary.

7.1.6 Assessment of Subject Compliance with the Study Visit Schedule

Study product will be administered to subjects by an unblinded study vaccine administrator via IM injection at all dosing times and as described in Section 4.3. Thus, subject compliance is not anticipated to be an issue. Deviations from the dose schedule may only occur as described in Section 4.4.

7.2 Laboratory Evaluations

7.2.1 Clinical Laboratory Evaluations

7.2.1.1 Baseline Screening Laboratories

Serum pregnancy tests will be performed locally by site laboratory at the screening visit and urine pregnancy test will be performed prior to each study vaccination on all women of childbearing potential. Results must be known and negative prior to randomization on Day 1 to be eligible for participation in this trial. Baseline laboratories will be obtained as defined in **Section 2.3.1**.

DMID/NIAID/NIH

7.2.1.2 Subsequent Testing Including Safety Laboratories

Urine pregnancy tests will be performed by locally by site laboratory within 24 hours prior to each study vaccination (Days 1, 29, and 180) on all women of childbearing potential. Results must be known and negative prior to administration of each study vaccination to be eligible for participation in the study and receipt of each dose of study vaccine, respectively. Safety laboratories will be obtained as defined in **Section 2.3.1**. Subjects will have follow-up safety laboratories obtained on Days 8, 36, 180, and 187 (about 13 mL).

Laboratory toxicities will be determined according to **Appendix B**. Laboratory reports must be assessed by a study clinician licensed to make medical diagnoses and listed on the Form FDA 1572 as the site principal investigator or sub-investigator, document this review, and record any abnormal laboratory value that represents an increase in toxicity grade post study vaccination on the AE page of the eCRF. The laboratory reports must be filed with the source documents. All events should be followed to resolution, or until reaching a clinically stable endpoint.

The volume of venous blood to be collected for clinical safety laboratory evaluations is presented in **Appendix A**.

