Safety Laboratories:

- Hematology
 - Complete blood count with differential (which will include white blood cells, ANC, AEC, hemoglobin, and platelets).
 - A WBC evaluation may include any abnormal cells, which will then be reported by the laboratory. A hematology evaluation may include abnormalities in the red blood cell (RBC) count and/or RBC parameters and/or RBC morphology, which will then be reported by the laboratory. In addition, any other abnormal cells in a blood smear will also be reported. Only clinically significant abnormal WBC, abnormal RBC, or any other abnormal cells in a blood smear will be reported as AEs. Relatedness and clinical significance for abnormal results will be entered on the Local Laboratory Results eCRF.
- Chemistry (fasting or non-fasting)
 - o Creatinine
 - Alanine aminotransferase (ALT)

Expected risks include pain, soreness, redness, warmth, swelling, firmness and itching at the site of injection. Other reactions may include fever, chills, rash, myalgias, nausea, headache, fatigue, malaise and arthralgias. As with other vaccines, an allergic reaction including anaphylaxis is possible. There may be other side effects from the study vaccinations, even serious ones that are not yet known.

Pre-Clinical and Phase I-III Data:

Pre-clinical toxicology studies included acute single dose toxicity in mice, repetitive injection toxicity and immunogenicity in rats, teratogenic and developmental toxicity studies in mice and rats, a local tolerability study in rabbits, and a systemic anaphylaxis study in guinea pigs with HEV-239.²¹ Administration of HEV 239 protein at multiples of clinically relevant doses in a relevant clinical formulation was well tolerated in mice, rats, and rabbits. No significant adverse effects were identified in single dose and short-term repeat dose studies. In a developmental study in the mouse there was a possible dose-related trend towards higher numbers of fetal resorptions and abnormal ossification was observed at the highest doses. However, in a second study in rats at a higher dose, no adverse effects of treatment were identified.²¹ No unexpected local tolerance issues were identified in any of the preclinical studies.

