3.3 Study Endpoints or Outcome Measures

3.3.1 Primary

- Determine the number of solicited local and systemic reactogenicity events from the time of study vaccination through D8 after each study vaccination.
- Determine the number of vaccine-related unsolicited adverse events (AE) from the time of each study vaccination through D29 after each study vaccination.
- Determine the number of clinical safety laboratory AEs at Day 8 after each study vaccination.
- Determine the number of vaccine-related serious adverse event (SAE) from the time of first study vaccination through 6 months after the last dose of vaccine.
- Determine the number of subjects showing ≥4 fold rise in serum HEV IgG concentration by ELISA from the baseline at Days 8, 15, 29, 36, 43, 57, 180, 187, 194, 208, and 360.

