8.2 Specification of Safety Parameters

Safety will be assessed by the frequency and severity of:

- 1. Serious adverse events (see Section 8.1.4) occurring from the time of the first study vaccination through the last study visit (Day 360).
- 2. Solicited Adverse Events (see Section 8.1.2) reactogenicity events occurring on the day of each study vaccination through Day 8 after each study vaccination:

DMID/NIAID/NIH

a) Injection site reactions including pruritus (itching), ecchymosis (bruising), erythema (redness), induration (hardness)/swelling, pain, and tenderness.

b) Systemic reactions including fever, feverishness (chills/shivering/sweating), fatigue (tiredness), malaise (general unwell feeling), myalgia (body aches/muscular pain exclusive of the injection site), arthralgia (joint pain exclusive of the injection site), headache, nausea, and vomiting.

- 3. Clinical safety laboratory AEs (see **Appendix B**) at Day 8 after each study vaccination. Parameters to be evaluated include WBC, ANC, AEC, Hgb, PLT, Cr, and ALT (Section 2.3.1).
- 4. Unsolicited Adverse Events (see Section 8.1.3) non-serious adverse events occurring from the time of the first study vaccination until Day 57 then from Day 180 through Day 208. Unsolicited AEs will be collected at all visits from the time of the first study vaccination until D57, then from Day 180 through 208. Any safety-related changes that occur post-vaccination during these timeframes and that represent an increase in grade must be recorded on the eCRF. Thereafter, recording will be limited to SAEs.

All Grade 1, 2, and 3 changes except for Grade 1 and 2 solicited adverse events must be assessed for relatedness to the study vaccination. The assessment of causality must be determined by a study clinician licensed to make medical diagnoses and listed on the FDA Form 1572 as the site principal investigator or sub-investigator.

8.3 **Reporting Procedures**

Solicited injection site and systemic reactogenicity events will be documented and reported from the time of each study vaccination through D8 after each study vaccination.

Unsolicited non-serious AEs will be documented and reported at all visits from signing of the ICF onwards until D57, then from Day 180 through Day 208.

SAEs will be collected from the time of the first study vaccination through the last study visit (Day 360).

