8.4 Type and Duration of Follow-up of Subjects after Adverse Events

Solicited AEs are reactogenicity events occurring on the day of each study vaccination through Day 8 after each study vaccination. Unsolicited AEs are non-serious adverse events occurring from the time of the first study vaccination until Day 57, then from Day 180 through Day 208. AEs will be assessed, and followed from initial recognition of the AE through end of the protocol defined follow-up period. AEs will be followed to adequate resolution. Resolution of an AE/SAE is defined as the return to pretreatment status or stabilization of the condition with the expectation that it will remain chronic.

DMID/NIAID/NIH

SAEs will be collected from the time of the first study vaccination through the last study visit (Day 360). SAEs will be followed to adequate resolution or stabilization even if this extends beyond the study-reporting period.

Follow-up procedures, evaluations, and outcomes will be recorded on the appropriate eCRF.

8.5 Procedures to be Followed in the Event of Abnormal Laboratory Test Values or Abnormal Clinical Findings

Samples will be collected for hematology, serum chemistry and urinalysis. The study clinician licensed to make medical diagnoses and listed on the Form FDA 1572 as the site principal investigator or sub-investigator must review the laboratory results, document this review, and record attribution to study product and clinical significance for all abnormal laboratory values on the Local Laboratory eCRF. Abnormal laboratory results meeting the protocol-defined toxicity grading scale are considered adverse events; however, they ARE NOT reported as unsolicited AEs on the Adverse Event eCRF. The laboratory reports must be filed with the source documents.

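### Protocol 7.2.1.2 and 8.5 send graded laboratory values to different forms, and the SAP has no rule for laboratory terms on the AE page, so the count of related unsolicited AEs depends on the section followed

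*Protocol*

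**What the plan says.** **Recording.** Protocol 7.2.1.2 requires the clinician who reviews the laboratory report to "record any abnormal laboratory value that represents an increase in toxicity grade post study vaccination on the AE page of the eCRF". Protocol 8.5, addressed to the same clinician at the same review, treats results that meet the toxicity scale as adverse events but says "they ARE NOT reported as unsolicited AEs on the Adverse Event eCRF". It asks the clinician to "record attribution to study product and clinical significance for all abnormal laboratory values on the Local Laboratory eCRF". Protocol 2.3.1 agrees with 8.5 on the form: "Relatedness and clinical significance for abnormal results will be entered on the Local Laboratory Results eCRF". It also makes an exception for smear findings: "Only clinically significant abnormal WBC, abnormal RBC, or any other abnormal cells in a blood smear will be reported as AEs". Protocol 8.2 (item 4) and SAP 4.5.1 (item 4) say that increases in grade go on the eCRF, without naming the form.

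**Endpoints.** Protocol 3.3.1 lists two separate primary safety endpoints that matter here. The second is "Determine the number of vaccine-related unsolicited adverse events (AE) from the time of each study vaccination through D29 after each study vaccination". The third is "Determine the number of clinical safety laboratory AEs at Day 8 after each study vaccination". For laboratory AEs, Protocol 8.2 adds: "Parameters to be evaluated include WBC, ANC, AEC, Hgb, PLT, Cr, and ALT".

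**Analysis.** SAP 9.3 includes all reported adverse events in the summaries. SAP 9.3.2 tabulates unsolicited AEs by system organ class and preferred term. Neither excludes laboratory terms. SAP Table 25 has separate rows for unsolicited and laboratory AEs, and laboratory results have their own displays (Tables 46-53 for chemistry, with Table 47 for hematology; Tables 56-67 for hematology).

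**The concern.** The two recording instructions cover the same values and contradict each other. Under 7.2.1.2, a vaccine-related rise in grade at Day 8 reaches the AE dataset as well as the laboratory dataset. Under 8.5 it reaches only the laboratory dataset. The SAP gives the programmer no rule for separating the two, so a primary safety count would be settled by which protocol section the site read. With 20 vaccinees, one such event is visible in the percentage. Someone reading only Table 25 or the endpoint total would not see that the extra event was a laboratory value already reported in the laboratory row.

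**Working it through.** The plan gives no figure on this point. Its only computed design figures are the probabilities of seeing at least one AE among 20 vaccinees, 1 - (1 - p)^20. All five reproduce (0.20, 1.98, 18.21, 87.84 and 98.85%), and they are not in question.

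**Step 1: follow one event.** Take a non-serious, vaccine-related laboratory result in a vaccinee, with a rise in grade, drawn at Day 8 after a dose.

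| Display | 7.2.1.2 followed | 8.5 followed |
|---|---|---|
| Second primary endpoint (related unsolicited AEs) | +1 | 0 |
| Table 25, unsolicited and related unsolicited rows | subject counted | not counted |
| Tables 39, 41, 42; Figures 19-20 | included | not included |
| Table 26, if the 5% threshold is met | included | not included |
| Table 45, if moderate or severe | listed | not listed |
| Table 25, laboratory row; laboratory tables | included | included |

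The second endpoint changes only for related results within Day 29 of a dose. That window covers the Day 8, 36 and 187 draws and any repeat at Day 15, 43 or 194. It does not cover the Day 180 draw before dose 3, because Day 29 after dose 2 is Day 57. Tables 39 and 41 are not limited to related events, so they change with any rise in grade entered on the AE page.

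**Step 2: size.** The endpoint is worded as a number of events, so each event adds 1. For subject incidence, with exact (Clopper-Pearson) limits and n = 20:

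- 0/20 = 0%: upper limit 1 - 0.025^(1/20) = 16.8%.
- 1/20 = 5%: lower limit 1 - 0.975^(1/20) = 0.1%; upper limit 24.9%.
- 2/20 = 10%: 1.2% to 31.7%.

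One added vaccinee moves 0/20 to 1/20, or 1/20 to 2/20 if one other vaccinee already has a related unsolicited AE. If the affected vaccinee already has such an AE, the event count rises by 1 and the incidence does not move. Tables 25 and 42 print no intervals, so the limits here only show the scale. The documents give no laboratory event rate, so no probability is attached.

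**Step 3: the third endpoint.** Protocol 8.5 makes any result on the toxicity scale an AE. Protocol 7.2.1.2 covers only an increase in grade. Inclusion criterion 5 (footnote 5) admits minor abnormalities that are not clinically significant, so a subject can enter at Grade 1. If that subject is still Grade 1 at Day 8, the result is a laboratory AE by the wording of 8.5 but is not recorded under 7.2.1.2. Protocol 8.1.1, which treats conditions present at screening as baseline, adds to the doubt. The text does not settle which definition the third endpoint uses.

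**The case against.** The strongest reply is that the design already resolves this in favour of 8.5. Protocol 8.2 and SAP 4.5.1 list laboratory and unsolicited AEs as separate items. Table 25 has a laboratory row. Tables 46-47 carry relationship, alternate etiology, action taken and discontinuation. Tables 51-53 and 62-67 tabulate related laboratory results. This stands as evidence of intent, but it does not stop a site from following 7.2.1.2, and it gives no rule for removing a laboratory term once it is on the AE page.

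A reader might infer from SAP 9.3 that laboratory events are meant to enter the unsolicited tables. The documents do not support that: reporting them in the laboratory tables satisfies the same sentence. The gap is the lack of a rule, not an instruction to include them.

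Protocol 8.2 refers to Section 8.1.3 for unsolicited AEs, and the copy reviewed shows no text under that heading. A definition there might help, but it would not remove the conflict between 7.2.1.2 and 8.5.

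It is also fair that any overlap can be traced by preferred term in Tables 39, 41 and 42, in Listing 10 and in Tables 46-47, and that the size shown is conditional. Both points limit the weight of the finding.

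**Conclusion.** The conflict is real and should be fixed. If 7.2.1.2 was followed and a laboratory value was judged related, each such event within Day 29 of a dose adds 1 to the second primary endpoint. In the illustration, incidence moves from 0/20 (0-16.8%) to 1/20 = 5% (0.1-24.9%), provided that the vaccinee has no other related unsolicited AE. The consequence is a descriptive misclassification. The trial tests no hypothesis, so no test is affected.

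Two stronger readings should be avoided. A reader might infer that laboratory events were in fact counted in both endpoints, but the documents do not show which section the site followed or that any related laboratory event occurred. A reader might also infer that the third endpoint is safe because laboratory results are reported separately in either case. That is not established, because 8.5 counts any graded result and 7.2.1.2 only an increase in grade. The plan should state which applies.

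**What to change.** 1. **Protocol.** Delete the AE-page instruction in 7.2.1.2 and point to the Local Laboratory eCRF, as 8.5 does. Name that form for laboratory values in Protocol 8.2 (item 4) and SAP 4.5.1 (item 4). State whether a laboratory AE is any graded result or only an increase in grade.

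2. **SAP 9.3.2.** Add: *Non-serious graded results in the safety laboratory parameters of SAP Table 6 are not counted in the unsolicited AE rows, tables and figures, even if entered on the AE page; they are reported in the laboratory row of Table 25 and the laboratory tables. Laboratory events meeting an SAE criterion stay in every display that includes serious events (Tables 25, 26 and 44, Figures 19-20). Clinically significant abnormal-cell findings on a smear (Protocol 2.3.1) remain unsolicited AEs.* The limit to non-serious results matters: a blanket exclusion would drop serious laboratory events from Table 26 and Figures 19-20.

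3. **Table 25.** Source the early-termination row from the laboratory form as well as the Adverse Event eCRF. Its footnote now cites only the latter, so a termination due to a laboratory result could be missed.

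The halting text (Protocol 8.6.1 and 8.6.2, SAP 6.6) lists laboratory and unsolicited events separately and must be reconciled with this wording; no change to it is proposed.

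**Cost.** Text changes and one footnote, with no new data. Unsolicited counts may fall. Laboratory entries already on the AE page must be flagged before lock. A related graded result first found outside Day 8 (the Day 180 draw, Days 15, 43 or 194, or an unscheduled visit) would count in neither endpoint, as already follows from 8.5. It would still appear in Tables 46-47 and the maximum post-baseline rows.
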